	3 APPENDICES	
14	4 ATTACHMENTS	35
2	15 SIGNATURES	36

Protocol/Amendment No.: 1.1 (14 Sep 2019)

VEAP ID NO: 8439

Epidemiology No.: EP05026.058

Sponsor Contact Information

The investigator will send study deliverables to: [name] MSD Taiwan OGMA [name] Phone: **Investigator Contact Information** [Name]TBD [Title] [Address] [Telephone]

Product: MK-3475
Protocol/Amendment No.: 1.1 (14 Sep 2019)
VEAP ID NO: 8439

Epidemiology No.: EP05026.058

PROTOCOL SUMMARY

Title	A post-licensure prospective observational registry study in real-world Taiwanese cancer patients with microsatellite instability-high (MSI-H) or deficient mismatch repair (dMMR) genes		
Vendor/Collaborator	To be determined		
Rationale	Pembrolizumab has demonstrated significant efficacy in clinical trials (protocol numbers KN158 and KN164) among MSI-H/dMMR patients with a diagnosis of advanced unresectable or metastatic solid tumors. The proposed study is to provide complimentary real-world data in a similar patient population after the approval of the pan-tumor indication for MSI-H/dMMR.		
Primary Objective(s)	 In an observational study in advanced MSI-H/dMMR cancer patients treated with pembrolizumab and followed prospectively, 1) describe demographic and clinicopathological characteristics; and 2) describe clinical outcomes of interest (objective response rate and duration of response). 		
Study Design	In major cancer centers in Taiwan, patients with a diagnosis of advanced unresectable or metastatic solid tumors who had progressed on prior standard therapy following index diagnosis will be screened for MSI/MMR status. Patients tested MSI-H (including deficient mismatch repair, dMMR), and have received at least one dose of pembrolizumab will be enrolled following consent and prospectively followed through a registry. Pre-specified clinical outcomes will be determined by qualified medical professionals in a standardized fashion and recorded.		
Study Population	A total of 20 patients with a diagnosis of advanced unresectable or metastatic, non-colorectal (CRC) solid tumors, who tested MSI-H, and had progressed after receiving prior standard therapy following the index diagnosis and then received at least one dose of pembrolizumab, will be included into the proposed study.		
Study Duration	The recruitment period is estimated to take at least 2 years, depending on the speed of uptake of pembrolizumab; and all patients who respond to the treatment of pembrolizumab will be followed through the registry for a minimum of 1 year following response to measure duration of response.		
Exposure and Outcome	The exposure of interest in the proposed study is treatment with pembrolizumab. The primary outcome is patient's response to pembrolizumab treatment (complete response, partial response, stable disease, or progression). Response to treatment will be assessed using Response Evaluation Criteria in Solid Tumors (RECIST) 1.1. Duration of response will also be described among those who respond to the treatment of pembrolizumab.		
Statistical Methods	Descriptive analyses will be performed to report the patients' characteristics, and objective response rate among patients received pembrolizumab. Specifically, frequencies with corresponding 95% confidence intervals will be used to describe the patients' characteristics. For clinical outcomes, proportion of the objective response rate and corresponding 95% confidence interval will be reported. Kaplan-Meier survival curves will be used to report the duration of response. If median		

Product: MK-3475
Protocol/Amendment No.: 1.1 (14 Sep 2019)
VEAP ID NO: 8439

Epidemiology No.: EP05026.058

	duration of response is reached within the study follow-up period, then it will also be reported.
Sample Size and Power Calculations	The study sample size was mandated by the Taiwanese regulatory agency. The proposed study will include 20 patients meeting the study inclusion/exclusion criteria. The 20-patient sample size produces a two-sided 95% confidence interval with a precision (half-width) equal to 19% for the response rate, assuming a 20% objective response rate.
Limitations	Because of the non-interventional nature of this study in a real-world setting, clinical visit schedules and tumor response assessment visits will be dependent on individual treating physicians with no pre-specified standards. Introduction of some variation in the measurement of clinical outcomes is possible. In addition, funneling and selection biases can potentially exist in this study, as inherent limitations in observational studies. However, the objective of this study is aimed to provide much needed information regarding pembrolizumab use in Taiwanese MSI-H cancer patients in the real world and is not meant to be compared directly to the clinical trial results.

VEAP ID NO: 8439

Epidemiology No.: EP05026.058

1 Background and Rationale

1.1 Background

1.1.1 PD-1/PD-L1 pathway in cancers and pembrolizumab

The PD-1 receptor-ligand interaction is a major pathway hijacked by tumors to suppress immune control. The normal function of PD-1, which is expressed on the cell surface of activated T-cells under healthy conditions, is to downregulate excessive immune responses, including autoimmune reactions. PD-1 (encoded by the gene *Pdcd1*) is a member of the Ig superfamily related to CD28 and CTLA-4, which has been shown to negatively regulate antigen receptor signaling upon engagement of its ligands (PD-L1 and/or PD-L2). [1,2]

Pembrolizumab is a highly selective humanized mAb that binds to the human PD-1 receptor and blocks the interaction between PD-1 and its 2 ligands: PD-L1 and PD-L2. The PD-1 pathway represents a major immune control switch that may be engaged by ligands expressed in the tumor microenvironment. High expression of PD-L1 on tumor cells has been found to correlate with poor prognosis and survival in various cancers. This PD-1/PD-1 ligand axis can be exploited to re-activate T cells and promote tumor cell destruction. By inhibiting the PD-1 receptor from binding to its ligands, pembrolizumab activates tumor-specific cytotoxic T lymphocytes in the tumor microenvironment and stimulates antitumor immunity.

1.1.2 Mismatch Repair Deficiency and Microsatellite Instability

1.1.2.1 Microsatellite Instability

Microsatellites are tracts of repetitive DNA in which certain DNA motifs (ranging in length from 1–6 or more base pairs) are repeated, typically 5–50 times [3]. These repetitive DNA sequences are more frequently copied incorrectly when DNA polymerases cannot bind efficiently to repair sequence errors that occur during DNA replication. Microsatellite instability (MSI) is the condition of genetic hypermutability that results from impaired DNA mismatch repair (MMR), or deficient (defective) MMR (dMMR). The presence of MSI represents phenotypic evidence that MMR is not functioning normally. MMR proteins include MLH1, MSH2, MSH6 and PMS2. They are responsible for recognizing and correcting errors in mismatched nucleotides and insertions/deletions. MSI usually arises from germline mutation in components of the MMR machinery; or somatic hypermethylation of the MLH1 promoter [4].

1.1.2.2 Detection of MSI/dMMR and relevant Guidelines

Protocol/Amendment No.: 1.1 (14 Sep 2019)

VEAP ID NO: 8439

Epidemiology No.: EP05026.058

In 1993, MSI was first linked to a subgroup of colorectal cancer (CRC) patients (hereditary nonpolyposis CRC, HNPCC; or Lynch syndrome), as well as a portion of nonhereditary (sporadic) colorectal tumors. The presence of MSI in tumor tissue was associated with unique clinical features and prognosis. Therefore, the need to develop uniform criteria for MSI or dMMR detection was growing [5].

In 1997, a U.S. National Cancer Institute workshop on MSI for cancer detection and familial predisposition, developed guidelines for international criteria for determination of MSI in CRC (the Bethesda guidelines) [5]. To ensure reproducibility and standardization, the guidelines recommended a reference panel of 5 microsatellites (the Bethesda panel), including two mononucleotide loci ((BAT 25 and BAT 26)) and three dinucleotide loci (D2S123, D5S346, D17S250), for detection of MSI. This testing is polymerase chain reaction (PCR)-based, and a shift in the size of at least two of the 5 microsatellite loci is defined as MSI-high (MSI-H); and a shift in the size of only one microsatellite locus is considered MSI-low (MSI-L) [5]. Subsequently, the Promega corporation has developed a now widely used alternative to the Bethesda panel (the MSI Analysis System), which has improved sensitivity over the Bethesda panel, especially for endometrial cancer [6]. Immunohistochemistry (IHC) is another approach by detecting MMR proteins (MLH1, MSH2, MSH6 and PMS2) to determine which MMR gene is likely mutated. If all MMR proteins present, it is unlikely that any of MMR gene is mutated. A loss of expression in ≥1 mismatch repair proteins was defined as dMMR. The IHC-based assay performance characteristics are comparable to those of MSI testing with a high concordance rate [7].

Genetic sequencing is an approach that is mostly used for research purposes. The massively parallel DNA sequencing technologies enable interrogation of MSI at more loci than the typically 5-7 genes included in the PCR- or IHC-based assays. However, these sequencing methods are not standardized and require substantially more resources, and thus are mostly used academically [8,9].

In clinical oncology practice, current MMR/MSI testing with either an MMR protein IHC-based assay or PCR-based MSI loci testing is used mainly in the management of CRC patients, as recommended by the, European Society for Medical Oncology, National Comprehensive Cancer Network (NCCN), and American Society of Clinical Oncology [10-12]. Per the ESMO guidelines (2016) MSI testing is recommended in the metastatic disease setting that can assist clinicians in genetic counselling [13]. The most recent NCCN guidelines recommend that MMR or MSI loci testing be performed for all patients with metastatic colorectal, gastric, and esophageal cancers. It should also be noted that this guideline recommends either IHC-based testing or PCR-based testing in clinical decision making, and that "IHC for MMR and PCR for MSI are different assays measuring the same biological effect" because "patients determined to have defective MMR status are biologically the same population as those with MSI-H status." As such, both tests are widely and readily available in the EU and the US for routine clinical testing of tumor samples for any cancer, CRC or non-CRC.

VEAP ID NO: 8439

Epidemiology No.: EP05026.058

1.1.2.3 Epidemiology of MSI-H/dMMR in cancers

Several recent publications that investigated the prevalence of MSI-H across different tumors showed that the prevalence varied widely by tumor type and by disease stage [8,9, 14, 15]. By examining genetic sequencing data across different cancers of all stages, several tumor types, including endometrial, colorectal, and gastric cancers, were consistently found with the highest prevalence of MSI-H, generally above 10% [8,9,14,15]. MSI-H is present in about 15% of all CRC (mostly sporadic) [5, 16-18]. For most other cancers, the prevalence of MSI was well below 5% [8,9,14,15]. A review article on the literature of MSI in different cancers also reported corroborative results showing higher MSI-H prevalence in the aforementioned three cancers [4].

[figure not shown]

Figure 1. MSI-H prevalence in recent publications testing MSI across different cancer types Data extracted from [8,9, 14,15].

A general pattern of lower prevalence of MSI-H in more advanced stage of cancer was observed in a study among more than 12,000 cancer samples representing 32 distinct tumor types [14]. In that study, the overall MSI-H prevalence in stages I-III cancers was 8%; and the prevalence in stage IV cancers was 4% [14]. Other studies also demonstrated the same patterns in various cancers. For CRC, a systematic review also suggested that MSI is more

Epidemiology No.: EP05026.058

common among stage II (~20%) than stage III (~12%) CRC and is even less frequent among stage IV (~4%) disease {[18]. In sporadic endometrial cancer that accounts for the vast majority of endometrial cancer, MSI-H is observed in 11-32% of the patients [8,9, 15, 19-22]. Studies that reported MSI-H specifically in patients with advanced stage endometrial cancer tended to report a lower MSI-H prevalence between 11-22% [19, 22-24]. Differential MSI prevalence by stage of cancer was also reported in gastric cancer. In a study with 1,990 Korean gastric cancer patients, the prevalence of MSI-H in stages I-III, and IV patients was 13.7% and 5.3%, respectively [24]. Similar findings were reported in a study with 250 Italian gastric cancer patients [15]. Another large study also reported 11% MSI-H prevalence in stages I-III gastric cancer patients, compared to 6% in stage IV patients [14].

One of these 4 papers further examined MSI prevalence in early vs. late stage within each cancer type, as shown in Figure 2 [14]. Virtually all late stage cancers reported a lower-than-5% MSI prevalence, except for endometrial and gastric cancers.

[figure not shown]

Figure 2. MSI-H prevalence by stage of disease and cancer type Data extracted from [14].

In summary, it is well recognized that the highest MSI-H prevalence is observed in colorectal, endometrial, and gastric cancers. In contrast, the prevalence of MSI-H in other cancer types is generally low, below 5%. In addition, the pattern of a lower MSI-H

Protocol/Amendment No.: 1.1 (14 Sep 2019)

VEAP ID NO: 8439

Epidemiology No.: EP05026.058

prevalence in advanced stage (IV) of cancer, compared to that in the earlier stage (I-III) of the disease is observed unequivocally across different cancer types.

1.1.2.4 Pembrolizumab MSI-H regulatory submission in Taiwan

The MSI-H application provides results from 2 clinical studies supporting the use of pembrolizumab for the treatment of patients with advanced MSI-H cancer in the 2L and higher settings.

Pooled efficacy and safety results from KEYNOTE-164 (subjects from Cohort A with MSI-H CRC) and KEYNOTE-158 (subjects with MSI-H non-CRC), referred to as the MSI-H population in this document, demonstrate that pembrolizumab treatment provides substantial clinical benefit with durable responses in subjects with MSI-H cancer across multiple tumor types, and that pembrolizumab treatment is safe and well tolerated in this patient population. Treatment with pembrolizumab therefore provides a meaningful improvement compared with available therapies. The aforementioned submission included 61 CRC and 94 non-CRC patients. The combined ORR was 33.5% (95% CI 26.2%-41.6%). Stratified analyses by CRC vs non-CRC reported an objective response rate of 27.9% (95% CI 17.1%-40.8%) and 37.2% (95% CI 27.5%-47.8%), respectively.

The approved indication for pembrolizumab in this application is for the treatment of patients with the following unresectable or metastatic MSI-H/dMMR cancers.

- colorectal cancer that has progressed following treatment with a fluoropyrimidine, oxaliplatin, and irinotecan, or
- solid tumors that have progressed following prior treatment and who have no satisfactory alternative treatment options [see Clinical Studies (12.8)].

This indication is approved under accelerated approval based on tumor response rate and durability of response. Continued approval for this indication may be contingent upon verification and description of clinical benefit in confirmatory trials

1.2 Rationale

Protocol/Amendment No.: 1.1 (14 Sep 2019)

VEAP ID NO: 8439

Epidemiology No.: EP05026.058

The purpose of this proposed multi-center, prospective, observational study is to complement the clinical trial data included in the submission by describing the effectiveness and safety of pembrolizumab use among advanced MSI-H patients with prior therapy history under real-world clinical practice conditions in Taiwan.

2 Objectives and Hypotheses

2.1 Primary Objective(s) & Hypothesis(es)

In an observational study in advanced MSI-H cancer patients treated with pembrolizumab and followed prospectively,

- 1) describe demographic and clinicopathological characteristics; and
- 2) describe clinical objective response rate and duration of response

2.2 Secondary Objective(s) & Hypothesis(es)

In an observational study in advanced MSI-H cancer patients treated with pembrolizumab and followed prospectively,

- 1) describe the treatment-emergent adverse events for pembrolizumab as reported during routine clinical care; and
- 2) if data allow, describe progression-free survival and overall survival as observed within the study period

3 METHODOLOGY

3.1 Summary of Study Design

In major cancer centers in Taiwan (number to be determined), patients with a diagnosis of advanced unresectable or metastatic non-CRC solid tumor (primarily focused on gastric and gynecological cancers), who have progressed after prior standard therapy following the index diagnosis, tested MSI-H (including dMMR), and received at least one dose of pembrolizumab will be identified. Patients with already determined MSI-H/dMMR status via IHC/PCR/NGS testing prior to study initiation will also be identified. These patients will then be enrolled and prospectively followed through a registry. Prespecified clinical outcomes will be determined by qualified medical professionals in a standardized fashion and recorded. Figure 3 depicts the high-level overall study design. The recruitment/enrollment period is estimated to take at least 2 years, and all enrolled

Protocol/Amendment No.: 1.1 (14 Sep 2019)

VEAP ID NO: 8439

Epidemiology No.: EP05026.058

patients who respond to the treatment of pembrolizumab will be followed for at least 1 year following the date of response or at the time of death, whichever occurs first, after enrollment. Based on the data submitted to Taiwanese regulatory agency, for CRC, the median PFS was 2.3 months, and median OS was not reached for up to 12+ months of follow-up; for non-CRC, the median PFS was 5.4 months, and the median OS was 13.4 months. Therefore, the 1-year minimum of follow-up following response date should be appropriate to capture the main clinical endpoints of interest.

[figure not shown]

Figure 3. Study design flow chart

*Not deceased, have measurable tumor at baseline, do not have hematologic or other primary malignancies, did not receive checkpoint inhibitors

3.2 Study Population

A total of 20 MSI-H/dMMR, non-CRC patients with an advanced solid cancer (primary focus will be gastric and gynecological cancers) diagnosis and a history of previous treatment will be included in this study. In the recruitment phase, we will work with investigators at major cancer centers in Taiwan to proactively identify eligible patients. MSI-H/dMMR status can be determined by any specific assays (IHC- or PCR-based) that are used in routine clinical practice. In addition, patients tested with next-generation sequencing (NGS) with a derived MSI-H status across all solid tumor types will also be considered to enrich the study population. The recruitment phase will be closed once 20 non-CRC patients are consented and included in the registry. It is estimated that at least

Protocol/Amendment No.: 1.1 (14 Sep 2019)

VEAP ID NO: 8439

Epidemiology No.: EP05026.058

2 years are needed for the patient identification, recruitment, and registration. The study is expected to commence in Q1 or Q2, 2020 and continue till Q4, 2025. However, the actual length of time needed will be dependent on the uptake of pembrolizumab in MSI-H/dMMR patients and actual recruitment rate.

Among the MSI-H cancer patient is identified to be potentially eligible, electronic health records (EHR) and medical charts may be used to further determine the eligibility of the patients, particularly regarding medical and treatment histories. Patients who already had an MSI-H/dMMR status determined via prior testing will be identified via EHR and medical records and patients who tests MSI-H/dMMR during the recruitment period will also be identified prospectively. These patients will be consented to be enrolled in the registry once they have received at least one dose of pembrolizumab as part of their clinical management and met other eligibility criteria. Patient selection for MSI/MMR tests will be up to the physician's discretion and clinical relevance. Clinical outcomes of interest as specified in the Objectives will be recorded according to pre-specified and standardized format, along with treatment emergent adverse events (TEAEs) as reported by either the patient or the treating physician. The follow-up of the patients will be at least 1 year from the response date of the patients who respond to pembrolizumab treatment.

3.3 Inclusion Criteria

- Adult (≥20 years) patients who met the approved MSI-H indication conditions
 - Had a diagnosis of advanced solid cancer
 - Had a history of prior standard treatment(s)
 - Had progressed on prior standard treatment(s) based on RECIST 1.1 or disease-specific tumor response measurement that are commonly used and accepted
- Were confirmed to be MSI-H through either specific MSI/MMR testing or NGS testing
- Received at least one dose of pembrolizumab
- Provided informed consent to participate in the study

3.4 Exclusion Criteria

- Had a diagnosis of hematologic cancer
- Had a diagnosis of CRC
- Already deceased at the time of identification
- Had received checkpoint inhibitors prior to the index diagnosis
- Have or had other primary malignancies

VEAP ID NO: 8439

Epidemiology No.: EP05026.058

4 Variables and Epidemiological Measurements

Data collection in this study will be based a combination of primary and secondary data. Briefly, leveraging the existing EHR systems in each of the cancer centers, if available, information on MSI/MMR testing results and previous medical history and selective baseline clinicopathological characteristics of the study population at enrollment will be extracted. Information that cannot be collected from the EHR system will be extracted from medical charts by trained medical chart extractors. Treatment history, clinical outcomes, and TEAEs following the administration of pembrolizumab will be collected by study staff prospectively.

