6.1.1 Administrative Procedures

6.1.1.1 MSI-H or dMMR identification

In collaboration with investigators at selective major cancer centers in Taiwan, we will identify eligible patients to be enrolled into the study through a combination of proactive identification and review of EHR and medical records. Medical records of identified patients will be reviewed to confirm prior specific MSI/MMR testing or NGS testing and MSI-H/dMMR status. Patients who did not have prior testing will be included if they have confirmed MSI-H status through MSI/MMR tests during the study period as advised by their physician. Patient selection for MSI/MMR tests will be up to the physician's discretion and clinical relevance. Patients will likely receive PCR-based tests performed by the hospital pathology department or as per other standard institutional processes (third party). Once a patient is confirmed to have MSI-H, and prescribed by the treating physician to receive pembrolizumab, the patient's EHR and/or medical charts will be further reviewed to ensure that the patient meets all inclusion and exclusion criteria. Once the eligibility is confirmed, the patient will then be enrolled in the study.

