9.1 Statistical Methods

The analyses will be of descriptive nature in this study. The study is not aimed to test any pre-specified hypothesis. All analyses will be performed by the sponsor or designee after the completion of the study and the study data files are locked and released.

9.1.1 Primary Objective(s): Calculation of Epidemiological Measure(s) of Interest (e.g. descriptive statistics, hazard ratios, incidence rates, test/retest reliability)

Descriptive analysis, including univariate analyses and cross tabulations, will be used for presenting baseline demographic and clinicopathological characteristics of the MSI-H/dMMR patients included in this study. Frequencies or mean and/or median will presented for discrete and continuous variables, respectively, with corresponding 95% confidence intervals (CIs). In addition, frequency of MSI/MMR testing method will also be presented to provide additional context.

ORR is defined as the combined proportion of patients with a CR or PR tumor response per the investigator's assessment, presented as a percentage with corresponding 95% CI. The primary analysis will be on combined ORR with all patients included in the study.

DoR is measured from the time of initial response until the time at which it is determined that tumor progression occurs. Kaplan-Meier plots will be generated to describe DoR with median DoR estimated along with the corresponding 95% CI.

Subgroup analyses in individual caner types for ORR and DoR will be performed only if adequate number (>5) of patients have the specific cancer.

9.1.2 Secondary Objective(s): Calculation of Epidemiological Measure(s) of Interest (e.g. hazard ratios, incidence rates, test/retest reliability)

TEAEs will be summarized for the study population using the NCI CTAE version 5. Frequencies with corresponding 95% CIs will be calculated by MedDRA system organ class (SOC), and worst

Protocol/Amendment No.: 1.1 (14 Sep 2019)

VEAP ID NO: 8439

Epidemiology No.: EP05026.058

CTCAE grade. These analyses will be performed for TEAEs, drug-related TEAEs, treatment-emergent SAEs, drug-related treatment-emergent SAEs, and TEAEs leading to dose modification, interruption, or permanent dose discontinuation.

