PFS is defined as the length of time between the day on which the first dose of pembrolizumab is given to the day on which PD is determined by the study investigator, or the day of death, whichever happens first. Kaplan-Meier plot will be generated to describe the PFS in the study population. Univariate analysis of PFS will be performed and the median PFS along with inter-quartile range will be reported with 95% CIs.

OS in this study is the length of time measured from the day on which the first dose of pembrolizumab is given to the day of death (of any cause). Similar analyses as performed for PFS will be performed for OS.

For PFS and OS, for patients with no events, the censoring date will be the last date of tumor response assessment performed and the last date the patient is seen alive during the study period. Subgroup analyses in individual caner types may be performed for PFS and OS, if there are at least >5 cancer patients in the subgroup.

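### Entry requires being alive at an uncapped time after the first dose, so OS (and, more weakly, PFS) from first dose carries immortal time and ORR is open to survivor selection

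*Protocol*

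**What the plan says.** **Entry.** Section 3.2 states: "These patients will be consented to be enrolled in the registry once they have received at least one dose of pembrolizumab". Section 3.3 requires that the patient "Provided informed consent to participate in the study", and section 3.4 removes those "Already deceased at the time of identification"; the footnote to Figure 3 repeats the requirement of not being deceased. Section 3.1 adds: "Patients with already determined MSI-H/dMMR status via IHC/PCR/NGS testing prior to study initiation will also be identified". Sections 3.2 and 6.1.1.1 describe finding such patients through electronic records and charts. Section 6.1.1.1 places the eligibility review at the point described as "Once a patient is confirmed to have MSI-H, and prescribed by the treating physician to receive pembrolizumab", followed by enrolment. None of these sections sets a maximum time from first dose to identification or consent.

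**Time origin.** Section 9.1.2 states: "OS in this study is the length of time measured from the day on which the first dose of pembrolizumab is given". For PFS: "PFS is defined as the length of time between the day on which the first dose of pembrolizumab is given". PFS is described by Kaplan-Meier, and OS is to be handled similarly. The only rule on time at risk is right censoring, at the last tumor assessment or the last date known alive.

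**ORR.** Section 9.1.1: "ORR is defined as the combined proportion of patients with a CR or PR tumor response per the investigator's assessment". It is a proportion of the included patients and has no time origin.

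**Bias.** Section 9.2.1 discusses funneling and selection, both towards sicker patients. Section 9.2.2 covers variable timing and assessment. Neither mentions selection of patients who survived long enough to be enrolled.

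**The concern.** The entry rule and the time origin do not fit together. A patient must be alive after the first dose to enter, but is counted as at risk of death from the first dose. Between the two dates no enrolled patient can die, yet the ordinary Kaplan-Meier estimate treats that interval as survival observed at risk. Patients who died in the same interval are absent from the data.

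The three outcomes are affected differently:

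- **OS:** the interval is event-free by design, so the bias is upward whenever the lag is positive.
- **PFS:** only death is excluded before entry. A progression before consent can still be counted, so the bias is upward but smaller.
- **ORR:** there is no clock. The exposure is in the denominator, which loses patients who died before they could be enrolled. ORR rises only if those patients were less likely to be responders.

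Because section 9.2.1 points only towards sicker patients, a reader of the report could take the results as conservative when this mechanism acts in the opposite direction.

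**Working it through.** **The plan's own figure.** Section 9.3 gives a 95% CI half-width of 19% for 20 patients at 20% ORR. Half the width of the exact (Clopper-Pearson) interval is 19.0%. For ORR of 10, 20, 30, 40 and 50% it is 15.2, 19.0, 21.2, 22.4 and 22.8%, against the stated 15, 19, 21, 22 and 23%. The figure reproduces. It measures sampling error, so it does not bear on the bias and serves below only as a yardstick.

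**Inputs from the protocol.** Non-CRC median PFS 5.4 months and median OS 13.4 months (section 3.1); non-CRC ORR 37.2% and planning ORR 20% (section 9.3).

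**Assumption.** The lag L from first dose to entry is not given. Values of 1, 3 and 6 months are shown, first as if every patient had the same lag.

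**OS, simple model.** With exponential survival, the rate is ln 2 / 13.4 = 0.0517 per month and S(L) = exp(-0.0517 L):

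- S(1) = 0.950, S(3) = 0.856, S(6) = 0.733, so 5.0%, 14.4% and 26.7% die before entry.
- The naive median t solves S(t) = S(L)/2, which gives t = 13.4 + L: 14.4, 16.4 and 19.4 months.

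**OS and PFS, illness-death model.** A constant death rate puts many deaths in the first months, so it is the high-end case. The alternative takes exponential PFS with median 5.4 months, lets 0, 15 or 30% of PFS events be deaths, and tunes exponential post-progression survival (means 8.2, 10.1 and 13.8 months) so that median OS is 13.4. Simulated medians among patients alive at L, with the clock at first dose:

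| Lag (months) | Naive median OS, illness-death | Naive median OS, exponential | Naive median PFS (true 5.4) |
|---|---|---|---|
| 1 | 13.5-14.1 | 14.4 | 5.5-5.7 |
| 3 | 14.1-15.5 | 16.4 | 5.8-6.4 |
| 6 | 15.8-17.8 | 19.4 | 6.9-7.5 |

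If lags are instead spread evenly over 0 to 6 months, the illness-death model gives a median OS of 14.3-15.5 and a median PFS of 5.9-6.4 months.

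**ORR.** Let q be the true ORR, and let Sr and Sn be survival to L in responders and non-responders, with q·Sr + (1-q)·Sn = S(L). S(L) is taken from the exponential model. The ORR among patients alive at L is q·Sr / S(L).

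- Equal mortality (Sr = Sn): the ORR stays at q.
- Responder hazard one third of the non-responder hazard (Sr = Sn^(1/3)): for q = 0.372 at 3 months, Sn is about 0.811 and Sr about 0.932, so the ORR is 0.372 × 0.932 / 0.856 = 0.405. At 6 months it is 0.440.
- No responder dies before entry (upper bound, Sr = 1): 0.372 / 0.856 = 0.434 at 3 months and 0.372 / 0.733 = 0.507 at 6 months.

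| True ORR | Lag (months) | Equal mortality | One-third hazard | Upper bound |
|---|---|---|---|---|
| 37.2% | 1 | 37.2% | 38.3% | 39.2% |
| 37.2% | 3 | 37.2% | 40.5% | 43.4% |
| 37.2% | 6 | 37.2% | 44.0% | 50.7% |
| 20% | 3 | 20.0% | 22.0% | 23.4% |
| 20% | 6 | 20.0% | 24.2% | 27.3% |

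**The case against.** The strongest reply is that the design is meant to be prospective and the lag may be short. Section 6.1.1.1 runs from confirmed MSI-H status to prescription, eligibility review and enrolment. Table 1 places consent in the screening column, and section 4 says that outcomes after pembrolizumab are collected prospectively. The sentence in section 3.1 on earlier testing concerns MSI status known before study start, not treatment begun before it. A patient followed along this path who dies in the third week would be enrolled and counted. At a 1-month lag the bias is 0.1 to 1 month of median OS and at most 2 points of ORR.

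This stands as an argument about size. It does not remove the defect, because these passages describe a sequence without setting a window, and nothing bars a patient already on treatment for months. A reader might infer that the protocol plans to enrol patients with a known response, or that no early death can ever be captured. The documents support neither; they only leave late entry open.

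It is also fair that OS and PFS are secondary and reported if data allow (section 2.2), that the study is descriptive, that comparison with the clinical trials is disclaimed, and that selection bias is named in general terms. The ORR shifts at one-third hazard, about 3 points at 3 months and 7 at 6 months, are small beside the 21-22 point half-width for ORRs of 30-40%. These facts lower the stakes, but a descriptive median OS still needs a risk set that matches its time origin, and the selection that section 9.2.1 names runs the other way.

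**Conclusion.** The concern holds in a limited form. OS from first dose carries immortal time, PFS carries it more weakly, and ORR is open to survivor selection. The direction for OS is certain for any positive lag. For ORR it depends on non-responders dying sooner, and with equal mortality there is no inflation.

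The size cannot be fixed from the protocol. If every patient had a lag of 1, 3 or 6 months, a true median OS of 13.4 months would read about 13.5-14.4, 14.1-16.4 or 15.8-19.4 months. The low ends come from the illness-death model with no deaths before progression, the high ends from exponential survival. An ORR of 37.2% would read 37.2-43.4% at 3 months and 37.2-50.7% at 6 months; the upper values assume that no responder dies before entry.

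A reader might go further and conclude that all three outcomes contain immortal time, or that they are materially inflated even when every rule is followed. The documents do not support that. ORR has no time origin, progression before consent still counts towards PFS, and prompt enrolment after the first dose complies with every rule and leaves little bias.

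**What to change.** - **Section 9.1.2:** pre-specify Kaplan-Meier with delayed entry for OS and PFS, each patient joining the risk set on the consent date with time still measured from first dose. Restrict this PFS analysis to patients progression-free at consent. Pre-specify a sensitivity analysis with the clock starting at consent. It should not be a fallback chosen after the risk sets are seen, because that would change the estimand in response to the data.
- **Section 9.1.1:** report ORR also for patients consented before their first post-dose tumor assessment.
- **Reporting:** give the distribution of the first-dose-to-consent interval.
- **Section 9.2:** name survivor selection and state that it acts in the opposite direction to the biases already listed.

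No new data are needed: treatment start dates are collected under section 4.1 and consent is dated under section 6.1.1.2.

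The cost is statistical. With 20 patients the early risk sets may be very small, and a single early death can move the curve sharply, so the early estimates will be wider and possibly unstable. The unadjusted curve should be shown alongside. The PFS restriction drops patients who progressed before consent. Delayed entry also assumes that entry time is unrelated to prognosis, and it cannot restore patients who were never enrolled, which is why the lag itself must be reported.
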